The endpoints for this objective will assess changes in patient's clinical assessments (e.g., laboratory assessments, vital signs) between the index date and key time-points following the index date (Table 6-1). The change in clinical assessments will be summarized as the number (%) of patients experiencing a change in each clinical assessment. Changes in clinical assessments from the index date will also be presented as shift tables. Growth and development information will also be summarized for patients who were aged <18 years at the time of first dose and until the age of 18 years.

Endpoints related to objective #10: Type, frequency, seriousness, and severity per CTCAE v4.03 criteria and causality assessments of treatment-emergent adverse events

The endpoint will report adverse events defined as the appearance of (or worsening of any pre-existing) undesirable sign(s), symptom(s), or medical condition(s) that occur during the study period. As much as possible, each adverse event will be evaluated to determine:

1. Toxicity grade
2. Duration
3. Relationship to the study treatment (i.e., not related, related, unknown)
4. Whether it is serious as per medical chart (seriousness and seriousness criteria established during the MAP)
5. Action taken with respect to study treatment (i.e. dose increased; dose not changed; dose reduced; drug interrupted; drug withdrawn)
6. If a concomitant medication or additional therapy was provided (for example diet for impaired glycemic control)
7. Outcome (i.e., not recovered/not resolved, recovered/resolved, recovering/resolving, recovered/resolved with sequelae, fatal, unknown)

Adverse events will be summarized as: the number (%) of patients experiencing each adverse event, (the number (%)) of patients experiencing any CTCAE grade 3 or higher adverse event, the number (%) of patients with serious adverse events, the number (%) of events related to treatment, the number (%) of patients who received a concomitant or an additional treatment

due to adverse event. For adverse events requiring dose interruption, the duration of interruption will be reported.

Adverse events will be coded using the Medical dictionary for regulatory activities (MedDRA) terminology. The latest available MedDRA version at the time of the analyses will be used.

The outcome of adverse events will be presented as the number (%) of patients with each outcome after any event (e.g., number [%] of patients that did not recover from any event).

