1.2 Study objectives

Primary objective

To describe the efficacy of alpelisib as measured by the proportion of patients with response (yes/no) at Week 24 or 6 months (+/- 4 weeks), defined by achieving at least 20% reduction from index date in the sum of measurable target lesion volume (1 to 3 lesions, via central review of imaging scans), provided that none of the individual target lesions have $\geq 20\%$ increase from index date and in absence of progression of non-target lesions and without new lesions.

Secondary objectives

1. To assess changes in the sum of measurable target lesion (1 to 3 lesions) volume over time
2. To assess changes in the sum of all measurable (target and non-target) lesion volume over time
3. To assess changes in the sum of all measurable non-target lesion volume over time
4. To assess the duration of response defined as the time from first documented response, to the date of the first documented disease progression or death due to any cause.
5. To assess type of medication and non-drug therapies (e.g., concomitant PROS-related medications, PROS-related surgeries, duration of treatment/response) over time
6. To assess changes in PROS symptoms and complications (e.g., chronic bleeding/leaking, pain) over time
7. To assess changes in functional status (e.g., work/school/pre-school attendance, mobility) over time
8. To assess changes in HRU (e.g., ER visits, hospitalizations) over time
9. To assess changes in clinical assessments such as laboratory evaluation, vital signs and physical findings over time
10. To assess the safety and tolerability of alpelisib

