Number of ER visits related to PROS	Continuous	N, mean, median, standard deviation, Q1, Q3, minimum and maximum	Overall during study period

Endpoints related to secondary objective #9: Change in clinical assessments such as laboratory evaluation, vital signs and physical findings over time

The following endpoints will assess changes in patient’s clinical assessments cardiac (e.g., ECG, BNP) and laboratory assessments (e.g., D-dimer, fibrinogen, hemoglobin) as well as vital signs (e.g., height, weight, blood pressure, pulse oximetry) between the index date and key time-points following the index date, appropriately by age groups.

The following summaries will be produced for laboratory data (by laboratory parameter):

- Worst post-baseline Common Toxicity Criteria (CTC) grade. Each patient will be counted only for the worst grade observed during study period.
- Shift tables using CTC grades to compare index date to the worst collected value during study period.
- For laboratory tests where CTC grades are not defined, shift tables using the low/normal/high/(low and high) classification to compare index date to the worst collected value during study period.

Vital signs assessments are reported in order to characterize basic body function. The parameters expected to be collected may include: height, weight, respiratory rate, systolic and diastolic blood pressure. The number and percentage of patients with notable vital sign values (high/low) will be presented. A listing of all vital sign assessments will be produced and notable values will be flagged.

Clinically notable vital sign criteria are provided [Table 3-8](#) below.

Table 3-8 Clinically notable changes in vital signs

Vital sign		Patient age at visit	
		< 18 years	≥ 18 years
Systolic blood pressure [mmHg]	High	≥ 95th percentile of the age and height group ¹	≥ 180 with increase from updated baseline ⁵ of ≥20 mmHg
	Low	≤ 5th percentile of the age and height group ¹	≤ 90 with decrease from updated baseline ⁵ of ≥20 mmHg
Diastolic blood pressure [mmHg]	High	≥ 95th percentile of the age and height group ¹	≥ 105 with increase from updated baseline ⁵ of ≥15 mmHg
	Low	≤ 5th percentile of the age and height group ¹	≤ 50 with decrease from updated baseline ⁵ of ≥15 mmHg
Oral body temperature [°C]	High	≥ 38.4°C	≥ 39.1°C
	Low	≤ 35.0°C	
Pulse rate [bpm] ²	High	2-3 years	> 128
		3-4 years	> 123

Vital sign	Patient age at visit				
		< 18 years	≥ 18 years		

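### For patients under 18, the SAP's vital-sign flags for blood pressure, pulse and respiratory rate record level only, and the protocol's shift tables and change counts for these signs are not carried into the SAP

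*SAP*

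**What the plan says.** SAP 1.2 gives secondary objective 9 as "To assess changes in clinical assessments such as laboratory evaluation, vital signs and physical findings over time". SAP 3.6 repeats that clinical assessments, vital signs included, are to be compared "between the index date and key time-points following the index date, appropriately by age groups".

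For vital signs SAP 3.6 then specifies two outputs. The first is a summary: "The number and percentage of patients with notable vital sign values (high/low) will be presented". The second is a listing: "A listing of all vital sign assessments will be produced and notable values will be flagged". The criteria stand in Table 3-8, titled "Clinically notable changes in vital signs" (the list of adverse-event groupings later in 3.6 carries the same table number).

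In the under-18 column of that table:
- Systolic and diastolic pressure are high at "≥ 95th percentile of the age and height group" and low at "≤ 5th percentile of the age and height group".
- Pulse and respiratory rate have fixed upper and lower limits by age band.
- Weight is judged by change from baseline.

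In the adult column, blood pressure and pulse require a level together with a change from an updated baseline. Adult respiratory rate is level-only.

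Protocol 6.8.2, under objective #9, names laboratory assessments and vital signs as its examples. It plans the number of patients with a change in each assessment, and adds: "Changes in clinical assessments from the index date will also be presented as shift tables".

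**The concern.** The objective and the table title speak of change, but three of the paediatric criteria use only the on-study value. A child already above the 95th percentile before the first dose is counted in the same way as a child who moves there on treatment.

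The protocol's own tool for telling these apart, the shift table, does not appear in the SAP for these signs. The study has a single arm, so no control group supplies a background rate, and Protocol 6.2.1 admits patients from age 2. A reader of the paediatric table would have to guess how much of each percentage was there beforehand. If every on-study record counts, part of each percentage also reflects how often the child was measured, which varies across sites in a chart review.

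**Working it through.** **Step 1: what each document specifies for paediatric vital signs.**

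| Item | Protocol 6.8.2 | SAP 3.6 |
|---|---|---|
| Number with a change | Yes, each clinical assessment | Weight only, through its change-based flag; none for blood pressure, pulse or respiratory rate |
| Shift table from index | Yes, clinical assessments | Laboratory data, height and BMI only |
| Time rule for the count | Key time-points | None stated for the notable-value count |
| Treatment of values already notable at index | Handled by the shift table | None |

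SAP section 2 declares only the two imaging-window changes. SAP section 1 presents the SAP as covering all analyses planned for the study report, so a table named only in the protocol has no specification to be produced from.

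**Step 2: background rate for one row with no drug effect.** Neither document gives a figure to reproduce. From the SAP: the upper limit is the 95th percentile, so a single reading in a reference child is flagged high with probability 5%. Table 3-1 gives three windows up to the 24-week time-point (4, 12 and 24 weeks) and five up to 52 weeks. Footnote 1 of the vital-sign table evaluates every blood pressure record. Assumed, because the documents do not say: children resemble the reference population, the within-child correlation rho is 0.3, 0.5 or 0.7, and the count takes any on-study reading.

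Model: z = sqrt(rho)·b + sqrt(1 − rho)·e, where b is the child's own level and e is reading-to-reading noise, both standard normal. A reading is high if z ≥ 1.645. Then

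P(at least one high in k readings) = 1 − E_b[ Φ((1.645 − sqrt(rho)·b) / sqrt(1 − rho))^k ].

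| Readings k | rho 0.3 | rho 0.5 | rho 0.7 |
|---|---|---|---|
| 1 | 5% | 5% | 5% |
| 3 | 13% | 12% | 10% |
| 5 | 19% | 17% | 14% |
| 6 | 22% | 19% | 15% |

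The limiting case of independent readings is 1 − 0.95^3 = 14% for three and 1 − 0.95^6 = 26% for six. By symmetry the low row behaves the same way.

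**Step 3: pre-existing abnormality.** Under the same model, a child who is high at baseline is flagged high again at least once in six readings in 51%, 65% and 78% of cases (rho 0.3, 0.5, 0.7). The planned count does not distinguish these children from new cases.

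**Step 4: what each remedy does.**
- *Excluding children already high at baseline, still over six readings.* The high-systolic rate falls from 22/19/15% to 21/16/11% (rho 0.3/0.5/0.7). This removes pre-existing cases but leaves most of the growth with readings.
- *One value per window, cross-classified by baseline status.* The expected share high in any window is 5%, however many readings were taken. Among children not high at baseline it is 4.5%, 4.0% and 3.2%.

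The per-window shift table therefore deals with both problems. The newly-notable count deals with only one.

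**The case against.** The strongest reply is that the plan already covers this. Protocol 6.8.2 promises the shift tables, and SAP section 2 does not withdraw them. SAP 3.6 states the intention to assess change, SAP 4.1 defines baseline and allows baseline data in safety summaries where appropriate, and every value is listed. This shows that the intention and the raw material exist. It does not supply the table: SAP 3.6 names shift tables for some assessments and not for these, and a listing is not a summary.

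Three stronger readings are tempting, and the documents do not support them.

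- *That most children would be flagged with no drug effect.* This needs systolic and diastolic, high and low, to be pooled over many readings. The SAP plans a high/low split, fixes no number of readings and does not say that any visit counts. Assuming a systolic-diastolic correlation of 0.5, a pooled blood pressure count over three readings is 42/39/34% (rho 0.3/0.5/0.7), which is below half throughout. A single high row stays at or below 22% up to six readings.
- *That the table could not show a drug effect.* With rho 0.5 and six readings, an upward shift of 0.5 SD moves the systolic high/low rows from about 19%/19% to 38%/7%, and a downward shift reverses them. The asymmetry would be visible.
- *That the adult rule shows how much a change condition would help.* The adult limits are also wider (pulse 50 and 120, against 58 and 92 from age 15), so a lower adult rate would not come from the change condition alone. For respiratory rate there is no adult contrast at all.

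**Conclusion.** The point holds in a limited form. For patients under 18, the blood pressure, pulse and respiratory rate flags are level-only under an objective and a table title about change. The SAP omits the protocol's change counts and shift tables for these signs without declaring it. As planned, the percentages mix new and pre-existing abnormality.

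The growth with readings is conditional, because the SAP states no time rule. If all on-study records count, the no-effect background for high systolic pressure is 5% at one reading and about 10-22% over three to six. That range rests on the reference-population assumption and a within-child correlation of 0.3-0.7. It is not extended to pulse and respiratory rate, because the documents do not say which centiles their age-band limits represent.

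The table would be harder to interpret than it need be, but it would still be readable. The severity is minor: this is a descriptive secondary safety summary with no hypothesis test and no bearing on the primary endpoint.

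**What to change.** Keep the Table 3-8 limits and add the following to SAP 3.6 for blood pressure, pulse and respiratory rate in patients under 18:

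1. The protocol's shift table: baseline status (low, normal, high) by status at each key time-point. Use the SAP 4.1 baseline and the single value per window from SAP 3.3, and show children without a baseline value on a separate line.
2. A stated time rule for the notable-value count: either any on-study record or one value per window. If any record counts, report the number of readings per child beside it.
3. Optionally, a supplementary row for newly notable values, meaning children whose baseline was not notable in the same direction. This row should not replace the shift table.

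If the omission was deliberate, declare it in SAP section 2 with the reason.

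The cost is one additional table from data already abstracted, with baseline and window rules already in the SAP. The downside is a smaller denominator where the baseline is missing. Some movement out of the abnormal baseline categories is also expected from regression to the mean, so upward and downward moves should be read together.

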Low		4-6 years	> 117	≥120 with increase from updated baseline ⁵ of ≥15 bpm	
		6-8 years	> 111		
		8-12 years	> 103		
		12-15 years	> 96		
		≥ 15 years	> 92		
		2-3 years	< 92	≤50 with decrease from updated baseline ⁵ of ≥15 bpm	
		3-4 years	< 86		
		4-6 years	< 81		
		6-8 years	< 74		
		8-12 years	< 67		
		12-15 years	< 62		
		≥ 15 years	< 58		
	Weight	High	increase from baseline ³ of ≥ 2 BMI-for-age percentile categories ⁴		Weight increase from updated baseline ⁵ of ≥ 10%
		Low	decrease from baseline ³ of ≥ 2 BMI-for-age percentile categories ⁴		Weight decrease from updated baseline ⁵ of ≥ 10%
Respiratory rate [breath per minute] ^{2,6,7}	High	2-3 years	> 34	≥30bpm	
		3-4 years	> 29		
		4-6 years	> 27		
		6-8 years	> 24		
		8-12 years	> 22		
		12-15 years	> 21		
		≥ 15 years	> 20		
	Low	2-3 years	< 22	≤ 10bpm	
		3-4 years	< 21		
		4-6 years	< 20		
		6-8 years	< 18		
		8-12 years	< 16		
		12-15 years	< 15		
		15-18 years	< 13		

bpm=beats per minute; NHLBI= National Heart, Lung, and Blood Institute;

¹ Blood pressure percentiles are calculated for each blood BP record using the method described in Appendix B of the following reference: The Fourth Report on Diagnosis, Evaluation and Treatment of High Blood Pressure in Children and Adolescents. Pediatrics 2004; 114; 555.

² Fleming S, Thompson M, Stevens R, et al. Normal ranges of heart rate and respiratory rate in children from birth to 18 years of age: a systematic review of observational studies. Lancet 2011; published online March 15. DOI:10.1016/S0140-6736(10)62226-X.

Vital sign	Patient age at visit	
	< 18 years	≥ 18 years
³ Baseline BMI-for-age weight status categories are underweight (less than the 5 th percentile), healthy weight (5 th percentile to less than the 85 th percentile), overweight (85 th to less than the 95 th percentile) and obese (equal to or greater than the 95 th percentile);		
⁴ BMI-for-age percentiles categories (P3, P5, P10, P25, P50, P75, P85, P90, P95, P97) are obtained from the WHO Growth Charts (http://www.who.int/childgrowth/en/);		
⁵ Updated baseline is the last value collected before the 18 th birthday.		
⁶ Eldridge L. What is a Normal Respiratory Rate?, Updated May 16, 2014;		
⁷ Kou .R., Shuei L., Bradypnea, Department of Physiology, School of Medicine, National Yang-Ming University, Taipei, Taiwan, http://rd.springer.com/referenceworkentry/10.1007%2F978-3-540-29676-8_246		

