Growth and development will only be summarized for patients who were aged <18 years at the time of alpelisib initiation.

BMI (kg/m²) will be calculated as weight [kg] / (height² [m²]). Individual trajectories for height and BMI will be compared to growth standards from the World Health Organization. Data are available online at (<http://www.who.int/childgrowth/en/>). Height and BMI will be summarized through the standard deviation score (SD- score), velocity and velocity SDS.

Z-scores or SD- scores are used to describe how far a measurement is from the median (average). The distribution of heights of all boys (or all girls) of a certain age follows a normal (or almost normal) distribution. The z-score of an observed point in this distribution is calculated as follows: Z-score (or SD-score) = (observed value - median value of the reference population) / standard deviation value of reference population. These scores are calculated differently for measurements that are distributed normally and non-normally in the reference population (Interpreting growth indicator, WHO. https://www.who.int/childgrowth/training/module_c_interpreting_indicators.pdf?ua=1)

Height and BMI SDS will be summarized using descriptive statistics (mean, standard deviation, range), as well as by presenting number of patients with SDS values lower/higher than 5th/95th percentiles respectively. Shift tables will be provided to compare index date to the last available value recorded during study period. Box plots may also be plotted for each time window.

Height velocity is defined as follows:

$$\text{Height velocity (cm/6-months)} = (\text{height in time window } k - \text{height in time window } k-1) \\ \div ([\text{assessment date in time window } k - \text{assessment date in time window } k-1] \div [365.25/2]),$$

and similarly for weight velocity.

Velocity SDS is calculated as (velocity – mean) / SD, where mean and SD are obtained as the height-, weight-, sex- and age-specific values in Tables 5 to 8 in Baumgartner et al (1986), where the age category immediately above the patient's exact age (at the assessment date in time window *k*) should be used. Velocity SDS will only be calculated for time window *k* if data also exists for time window *k-1*, since calculating across multiple units of 6 months requires more than one reference value to be taken into account.

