Height/weight SDS and velocity SDS will be summarized using descriptive statistics (mean, standard deviation, range) for each time window, as well as by presenting number of patients with SDS values lower/higher than 5th/95th percentiles respectively. Box plots will also be plotted for key time points.

Endpoint #10: Type, frequency, seriousness, and severity criteria and causality assessments of treatment-emergent adverse events.

Adverse events summary tables will report only on-treatment assessments/events (more details in [Appendix](#)). An on-treatment adverse event is defined as any adverse event reported in the following time interval (including the lower and upper limits):

- date of first administration of study treatment; date of last administration of study treatment + 30 days or cut-off date whichever occurs first

The endpoint will report adverse events defined as the appearance of (or worsening of any pre-existing) undesirable sign(s), symptom(s), or medical condition(s) that occur during the study period. The full population will be used for reporting Adverse Events (AE) and all safety endpoints. As much as possible, each AE will be evaluated to determine:

- Toxicity grade
- Impact (“Low”, “Medium” and “High”)
- Duration
- Relationship to the study treatment (i.e., not related, related, unknown)
- Whether it is serious as per medical chart
- Action taken with respect to study treatment (i.e. dose increased; dose not changed; dose reduced; drug interrupted; drug withdrawn). If a concomitant medication or additional therapy was provided (for example diet for impaired glycemic control)
- Outcome (i.e., not recovered/not resolved, recovered/resolved, recovering/resolving, recovered/resolved with sequelae, fatal, unknown)

All AEs collected in the AE eCRF page will be listed along with the information collected on those AEs e.g. AE relationship to study drug, AE outcome etc.

AEs will be summarized by number and percentage of patients having at least one AE in each primary system organ class (SOC) and for each preferred term (PT) using MedDRA coding. A patient with multiple occurrences of an AE will be counted only once in the respective AE category. A patient with multiple CTCAE grades (version v4.03) for the same preferred term will be summarized under the maximum CTCAE grade recorded for the event. AE with missing CTCAE grade will be included in the ‘All grades’ column of the summary tables.

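### The under-18 weight flag cannot register loss in a child who starts below P5 or gain in one who starts at or above P95, and its threshold varies with starting position

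*SAP*

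**What the plan says.** The rule is the Weight row, under-18 column, of the SAP table on clinically notable changes in vital signs (section 3.6, secondary objective #9). High is an increase, and Low a decrease, of two or more "BMI-for-age percentile categories" from baseline. Two footnotes are attached:

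- The one marked on the word baseline begins "Baseline BMI-for-age weight status categories are underweight" and goes on to four weight-status levels, divided at P5, P85 and P95.
- The one marked on the percentile categories reads "BMI-for-age percentiles categories (P3, P5, P10, P25, P50, P75, P85, P90, P95, P97) are obtained from the WHO Growth Charts".

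The SAP does not say how the two footnotes relate, whether the ten percentiles are cut lines or category labels, or where values below P3 and above P97 belong.

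From age 18 the row switches to relative change. The Low entry begins "Weight decrease from updated baseline" and requires at least 10%.

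The flag has two uses: "The number and percentage of patients with notable vital sign values (high/low) will be presented", and "A listing of all vital sign assessments will be produced and notable values will be flagged". Separately, the growth text of the same section derives height and BMI SDS for patients under 18 at alpelisib initiation, and states that "Height/weight SDS and velocity SDS will be summarized using descriptive statistics" for each time window.

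**The concern.** A rule that counts category steps on a bounded scale runs out of steps at both ends. Here the scale stops at P3 and P97 and the rule needs two steps, so children who start near either end may have no route to a flag whatever their weight does. The categories also differ in width on the SD scale, so the same two steps mean different amounts of change for different children.

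At stake is the reading of one safety percentage. Nausea, vomiting and diarrhoea form an adverse-event grouping of special interest in the SAP, and growth information for patients under 18 was added by protocol amendment, so weight change in children is something the report is meant to show. A count that structurally leaves out some children, and flags others on small changes, is hard to interpret.

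**Working it through.** The plan gives no figure for this rule, so there is none to reproduce. The check counts the available steps and then measures them.

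**Inputs.** Cut lines P3, P5, P10, P25, P50, P75, P85, P90, P95 and P97, and a minimum shift of two categories, both from the SAP table. Percentiles are converted to SDS by the standard normal quantile z; this is an assumption about the scale, not a figure in the plan.

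**Step 1: reachability.** Ten lines make 11 bands.

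- Baseline below P3: no band beneath. Baseline P3 to below P5: one band beneath. Two steps down are impossible, so Low is unreachable from any baseline below P5.
- Baseline P95 to below P97: one band above. Baseline at or above P97: none. High is unreachable from any baseline at or above P95.

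If the ten percentiles are instead ten category labels, Low is unreachable below P10 (label is the line below), up to P5 (line above) or up to P7.5 (nearest line). High is unreachable from P95, from just above P90, or from about P92.6, respectively. The floor below P5 and the ceiling from P95 hold on every one of these readings.

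**Step 2: size of the fall needed for Low (11 bands).** From a band whose lower edge is line k, the child must fall below line k−1. Fall needed = z(start) − z(line k−1).

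Quantiles: z(P75) = 0.674, z(P85) = 1.036, z(P90) = 1.282, z(P95) = 1.645, z(P97) = 1.881. The lower lines are the negatives of their mirror images.

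| Baseline band | Must fall below | Fall at lower edge (SD) | Fall just under upper edge (SD) |
|---|---|---|---|
| P5–P10 | P3 | −1.645 + 1.881 = 0.24 | −1.282 + 1.881 = 0.60 |
| P10–P25 | P5 | −1.282 + 1.645 = 0.36 | −0.674 + 1.645 = 0.97 |
| P25–P50 | P10 | −0.674 + 1.282 = 0.61 | 0 + 1.282 = 1.28 |
| P50–P75 | P25 | 0 + 0.674 = 0.67 | 0.674 + 0.674 = 1.35 |
| P75–P85 | P50 | 0.674 − 0 = 0.67 | 1.036 − 0 = 1.04 |
| P85–P90 | P75 | 1.036 − 0.674 = 0.36 | 1.282 − 0.674 = 0.61 |
| P90–P95 | P85 | 1.282 − 1.036 = 0.25 | 1.645 − 1.036 = 0.61 |
| P95–P97 | P90 | 1.645 − 1.282 = 0.36 | 1.881 − 1.282 = 0.60 |
| Above P97 | P95 | 1.881 − 1.645 = 0.24 | no upper limit |

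Among the bounded bands the requirement runs from about 0.24 to 1.35 SD, a ratio of 1.35 / 0.24 ≈ 5.6. The top band is open: from +3.5 SD the fall needed is 3.5 − 1.645 = 1.86 SD, and from +4 SD it is 2.36 SD. The rise needed for High is the mirror image.

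**Step 3: the same in percent weight (illustration).** Assume normal BMI with a coefficient of variation (CV) of 8% to 15%, and fixed height and age. Loss needed = 1 − (1 + CV × z(target)) / (1 + CV × z(start)).

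- Start P7: flagged after a loss of 3.7% to 7.8%.
- Start P50: flagged after 5.4% to 10.1%.
- Start P90: flagged after 1.8% to 3.1%.
- Start P3.9: a 10% loss takes the child to about P0.2 to P1.2, one band down, so no flag.

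**The case against.** The strongest reply is that nothing is lost from the report. Every vital sign is listed. Individual height and BMI trajectories are compared with WHO standards, and BMI SDS is summarised with counts beyond the 5th and 95th percentiles and shift tables to the last value. Weight SDS and velocity SDS are also tabulated. Protocol section 6.8.2 (objective #10) has undesirable signs found on vital signs captured as adverse events. This stands, and it limits the harm: a reader might infer that weight loss in the lightest children would be invisible, and the documents do not support that. But these outputs do not repair the flag. A count of children below the 5th percentile cannot show further loss in one already there, a shift table to the last value can miss an earlier low, and a mean can mask an individual fall.

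A second reply is that the two footnotes do not truly conflict. The footnote markers support this: the four-level footnote is attached to baseline, the ten-percentile footnote to the unit of shift. A reader might count shifts on the four levels and infer that no child below P85 could be flagged Low. That uses the scale not marked for shifts and should not be reported as the size of the problem. What remains is that the SAP should state the relation.

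A third reply is that this is one row of a descriptive table with no hypothesis test. That is correct and sets the weight of the point.

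**Conclusion.** The point holds as a fault in the rule rather than a missing detail: applied exactly as written, it cannot count certain children. It applies to children below P5 (Low) or at or above P95 (High) at baseline, and only at visits before age 18. A child who starts at P5 or higher and then falls far enough is flagged, and the 10% rule takes over from age 18.

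For the other children the Low threshold runs from about 0.24 to 1.35 SD among bounded bands and has no upper limit above P97, so 1.35 SD should not be quoted as the overall maximum. A reader might infer that the percentage reflects starting position alone; it reflects both starting position and amount of change.

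The number of patients affected is unknown, because the documents give no baseline BMI distribution. As an illustration only, if all 50 patients assumed in Protocol section 6.6 were children following the reference distribution, about 5% × 50 = 2.5 would start beyond each end. Nothing in the documents shows whether the true share is higher or lower. The primary endpoint is not affected.

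**What to change.** Base the under-18 weight flag on a change in BMI SDS from baseline, with the same threshold for every child and in both directions; or keep the category flag and report the SDS-based count beside it. The sponsor's safety team should set the threshold without reference to the observed weight data, and the SAP should record that.

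In the footnotes, state that the four-level set only describes baseline weight status and that the ten-percentile set is the unit of shift. Say whether the percentiles are cut lines, and how values below P3 and above P97 are classed. If the category flag stays, note under the table that Low is unreachable from below P5 and High from P95 upward.

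Do not carry the adult 10% weight-gain rule over to children: ordinary growth could trigger High, and the time windows run past 52 weeks.

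The cost is one changed or added table row and a footnote; BMI SDS is already derived. The downside is some loss of comparability with tables that use the category rule, which reporting both counts would avoid.
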